**C1a. Study Overview.** Research demonstrates that diabetes remission is achievable through weight loss, but pragmatic approaches that leverage existing staff and resources in the healthcare setting to deliver intensive behavioral lifestyle modification interventions are underdeveloped and underutilized. Our goal is to assess the effectiveness of an intensive multi-component plant-forward healthy eating intervention for patients with obesity-associated T2D. Our approach builds on the results of the Diabetes Remission Clinical Trial (DiRECT) study, and the preliminary results of the Management of Diabetes in Everyday Life (MODEL) study, to test a culturally tailored multicomponent intervention designed for a U.S. medically underserved population. This research design is an individually randomized controlled trial in 72 patients with obesity-associated T2D. The Healthy Eating and Active Living to Treat Diabetes (HEAL Diabetes) Study will assess a “full-court press,” clinic-based intervention with these evidence-based components: 1) **Intensive preparation for change** to a plant-forward healthy eating program for weight loss, 2) **Motivational interviewing-based health coaching (MI-based HC)** support for healthy eating and physical activity, 3) **Tailored motivational text messaging** from the health coach, 4) **Total diet replacement (TDR)** with healthy food boxes for 3 months, 5) **Health coach-led support groups**, 6) **Cooking classes**, and 7) **Physician-supervised medication discontinuation (PSMD)**. All components will be individually and culturally tailored to address social determinants of health serving as key barriers to healthy eating and physical activity. The U.S. Preventive Services Task Force concluded that adults with obesity benefit most from behavioral weight loss interventions that are intensive and multicomponent. MI-based HC has been demonstrated to be among the most effective component interventions for weight loss. Our team has extensive expertise implementing these interventions in the settings where low-income individuals with T2D and other obesity-associated chronic conditions receive routine care through the DiRECT, our MODEL, SafeMed, and other studies. DiRECT used health coaching in primary care practices, intensive preparation for change, TDR, and PSMD to achieve an average weight loss of 10.0 kg, diabetes remission in 46% at 1 year, sustained remission in 36% at 2 years, and improvements in key biological health outcomes at low cost. Best evidence suggests that these are among the components with the most potential to achieve similar outcomes in other at-risk populations. Preliminary results from the MODEL study indicate that primary care-integrated MI-based HC is well received, with highest self-reported levels of improvements in health behaviors, confidence, and health outcomes in the MI-based HC group, and overall retention of over 90% in 672 program participants. By directly supporting patients in achieving their health goals, MI-based HC is more effective at engaging patients in self-care than traditional diabetes education or weight loss classes. Furthermore, health coaches integrated into practices are increasingly sustainable due to the growth of value-based payment initiatives.

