**Table 1: Program Interventions by Group\***

Intervention Components	Multicomponent Intervention Group (Treatment)	Core Intervention Group (Control)
1) Intensive Preparation for Change and Education on plant forward healthy eating for weight loss	Guidebook, handouts	Guidebook, handouts
	Two (introductory and kickoff) health coach and nutritionist/registered dietitian co-led sessions with intensive preparation for dietary change & weight loss	One traditional diabetes education session led by a pharmacist or nutritionist/registered dietitian
2) Health Coaching - Motivational and educational support for healthy eating, physical activity, and weight loss	Individual HC sessions bi-monthly for first 3-4 months (Intensive Phase) and monthly for remaining 7-8 months (minimum of 14 sessions total)	–
	Health coach-led individual or group grocery store tours with individual patient reminders	–
3) Tailored motivational text messaging (TM)	Scheduled Registry-based TM and occasional individual TM from their health coach	–
4) Diet Replacement	Total diet replacement for months 2-4 using tailored healthy food boxes with recipes delivered weekly	Partial diet replacement for months 2-4 using grocery store produce vouchers
5) Support Groups	Monthly clinic-based, health coach-led or co-led sessions focused on MI-based group problem solving (added individual patient text and/or phone reminders)	–
6) Cooking Classes	Free monthly cooking classes with individual patient text and/or phone reminders	–
7) Physician-Supervised Medication Discontinuation	Baseline and follow-up physician visit (month 1 and month 2-4) with standardized instructions and protocol for partial medication discontinuation	Physician made aware of program participation and patients informed of need to discuss medications with physician

\* See **Sustainability Plan** and **Facilities** for details on sustaining organizations and sustainability plans for each intervention.

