**Non-responders**. Data including age, gender, body weight and height, and duration of diabetes will be recorded for all patients found to satisfy recruitment criteria upon screening who decline to participate. We will record reasons for non-participation. Characteristics of non-responders will be compared with those of participants to identify any recruitment bias, assess the representativeness of study participants, and help establish generalizability of the trial findings.

**C4d. Randomization Strategy.** Eligible participants will be randomized in a 1:1 ratio using a block design with blocks of size 8. We will select the block sequence at random and fill blocks of 8 before selecting a new block. This will guarantee approximately the same number of participants in each group throughout the trial. The SAS program will be used for implementing the randomization scheme. Randomization logs will be created by [name] and uploaded to the REDCap system. The study staff will use the REDCap system to randomize patients to either the Intensive Care (Treatment) group or Enhanced Care (Control) group. Study personnel who collect and manage data will be blinded to participants' treatment assignments.

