**C4e. Sample Size, Power, and Attrition.** This trial aims to recruit a sample of 72 (36 in each group), which is a pragmatic decision based on the patient pool, budget, and two-year study period. We will recruit patients from the Health Hub and Tennessee Population Health Data Network (TN- POPnet). Given the study has broad eligibility criteria, we anticipate an estimated 20 adult patients with diabetes and obesity being eligible each month. This will provide a sufficient pool to enroll 8 patients/month and 72 patients over 9 months. We expect that after accounting for 15% attrition at 12-month follow-up, about 61 study participants will complete the study. The attrition rate is based on the evidence from our MODEL study and from Lean *et al.* This pilot study will help us to estimate the following: 1) Effect size for the study intervention, 2) Total number patients recruited, 3) Number of patients recruited each month, 4) Total time required to recruit patients, 5) Number of patients retained, and 6) Barriers and facilitators to recruitment and implementation of the interventions. The research will employ intensive *scientific rigor* in every stage of design and conduct to ensure robust and unbiased experimental design, methodology, analysis, interpretation, and reporting of results and the ability to reproduce the research findings.

**C5. Multicomponent Motivational Interventions.** All component interventions received by both the treatment and control groups will be delivered in phases as shown in **Table 2** below.

**C5a. Intensive Preparation for Change and Core Educational Interventions.** All patients will receive introductory education on plant-forward healthy eating for weight loss. Health coaches will lead two sessions (introductory and kickoff) for the treatment group; pharmacists or nutritionists will lead one traditional diabetes education session for the control group. All patients will receive evidence-based self-care tools included in the MODEL program toolkit adapted from DPP, ACT, Look AHEAD, and TARGIT, and supplemental recipe and diet information adapted from DiRECT and the Daniel Diet program. Treatment group participants will also receive training in cognitive behavioral strategies employing these tools.

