Phase 1 (preparation phase) educational sessions for both groups will focus on introduction to and preparation for initiating plant-forward healthy eating. But in the treatment group, participants will be supported in preparing to strictly follow a low-calorie plant-forward weight loss diet (approximately 800 to 1200 kcal/d). Recommended diet characteristics are detailed below (**C5d. Diet Replacement**). Treatment group participants will be encouraged to track their adherence to prescribed low-glycemic diets with < 30% of calories from fat (< 10% from saturated fat) via easy-to-use logs. For the treatment group health coaches will help participants tailor their meals to their goals and preferences and TM will recommend similar meals. For both groups, emphasis will be placed on eating more fruits, vegetables, and other high-volume, low-energy-density foods. Continuous 30-minute moderate physical activity on over five days per week will be recommended.

**C5b. Health Coaching.** Participants in the treatment group will have their first individual session with their assigned health coach immediately after the baseline (randomization) visit. Health coaches will prioritize establishing rapport with the participant and identifying their motivations and initial goals using MI. HC program goals, plans for future individual sessions, and a written copy of their personal health goals will be given to them at the end of the session. Participation in the treatment arm will be monitored and supported by the assigned coach. The MI-based HC intervention will use MODEL toolkit content as described above. HC will aim to meet with participants for individual HC sessions bi-monthly the first month (Preparation Phase-2 sessions following randomization) and throughout Phase 2 (TDR) for 3 months (6 sessions total).

Components of HC will be personalized to each patient based on: patient preferences for frequency of contact and setting (in-clinic, telephone, home visit, or community); stage of disease (regimen complexity, complications, etc.); and patient-identified health goals, needs, motivations, and barriers to change.

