### **C8. Study Visits.**

Screening Visit. Eligibility will be assessed. A1c will be obtained from through a blood draw (less than 1 teaspoon of blood) through a finger stick. [name] will assay the patient's sample for HbA1c using the analyzer in the UT Endocrinology Lab to assess potential eligibility. In addition, patient's weight, height, BMI, and blood pressure will be measured using the scales the appropriate scales and validated protocols. Participants will also be required to provide a list of their current medications and name and contact information of the primary care provider in event that they are randomized into the intervention arm at the baseline visit. Participants will be informed of their rights to determine who has access to their personal health information (PHI) in compliance with HIPPA regulations. As part of informed consent patients will be extensively counseled regarding all components of the treatment and control interventions to confirm their interest and willingness to participate in all component interventions prior to enrollment. After informed consent, contact and demographic information will be obtained. If a study participant has difficulty reading the informed consent or other study data collection forms, project personnel will assist. At this visit, all baseline study measures will be obtained.

Baseline Visit. Following confirmation of eligibility at the screening visit, potential participants will be scheduled for a baseline visit at the health hub. Eligible participants will be randomly assigned to one of the two arms and informed of their group assignment. Participants will be randomized to the HEAL Diabetes arm or the usual care condition. We will randomize 20-24 participants for each recruitment wave, for a goal of approximately 12 per condition. Participants will be randomized 1:1 to the two study conditions in randomly permuted blocks of size 8 using SAS random allocation. The randomization list was generated through SAS at the start of the study before randomization. The list is managed by one of the PIs. Once a participant has been determined to be eligible, the PI will assign each participant to the next open assignment on the list. We will tell

them at the Baseline visit which group they were assigned. Additionally, participants will have their first introduction to the health coaches.

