**Other Factors.** Covariates will be measured at baseline. These will include demographic characteristics, marital status, education level, insurance, chronic conditions, and SDOH (using electronic health record data collected on all Health Hub clients), and health literacy. At baseline, 6-, and 12-month visits, we will assess prescribed medications. Exposure to each component intervention will be assessed using health coach attendance logs.

**C11. Analysis.** We will evaluate the extent to which the program was implemented according to the protocol, examine if all components of the intervention were delivered in a standardized and reproducible format, and summarize the trial as a flow diagram following Consolidated Standards of Reporting Trials (CONSORT) guidelines. Patient characteristics will be compared between study groups to assess integrity of the random assignment process. Data will be presented as means and standard deviations for continuous variables and as frequencies and percentages for categorical variables. Results will be analyzed based on intention-to-treat.

For Aim 2, we will use baseline, 6-, and 12-month follow-up data to compare differences between treatment and control group means in continuous primary biological outcomes (body weight, blood pressure, and A1c) and secondary patient-reported outcomes (self-care activities related to general diet and exercise). We will use the MIXED procedure of SAS because this is a parallel groups trial with repeated measures assessed over time. In the context of repeated measures ANOVA, we will use t-tests within group to detect change from baseline to 12-months (Follow-up 3) and t-tests between groups to detect the effect of the treatment on the various outcome variables at 12-months. While the preceding hypothesis tests are *a priori* and not adjusted, other comparisons at the intermediary assessments will be adjusted using the Bonferroni method. To examine a difference in the proportion of patients who achieved diabetes remission at 12-month, we will use a chi-square test.

For Aim 1, we will assess intervention operational sustainability as detailed above and in **Table 3**. Based on MODEL study experience providing MI-based HC and TM interventions, we hypothesize that operational sustainability will be high with 12-month program retention rates of approximately 85-90%.

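### C11 does not say how clustering by coach or support group in the treatment arm will be handled; if outcomes correlate within those groups, the between-arm and within-treatment standard errors are understated

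*Combined protocol and SAP*

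**What the plan says.** **Design.** C1a states: "This research design is an individually randomized controlled trial in 72 patients with obesity-associated T2D". C4d adds: "Eligible participants will be randomized in a 1:1 ratio using a block design with blocks of size 8". On size, C4e says "This trial aims to recruit a sample of 72 (36 in each group), which is a pragmatic decision"; it gives no power calculation. On dropout it says "We expect that after accounting for 15% attrition at 12-month follow-up, about 61 study participants will complete the study". The first quantity it lists for the pilot to estimate is the effect size of the intervention.

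**Delivery.** The Baseline Visit text in C8 says "We will randomize 20-24 participants for each recruitment wave, for a goal of approximately 12 per condition". For support groups, Table 1 gives the treatment arm "Monthly clinic-based, health coach-led or co-led sessions focused on MI-based group problem solving" and gives controls none. Table 2 adds two co-led introductory sessions in month 1, again for the treatment arm only. On coaching, C5b says "Participation in the treatment arm will be monitored and supported by the assigned coach". Controls get one education session and produce vouchers.

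**Analysis.** For the continuous Aim 2 outcomes, C11 says "We will use the MIXED procedure of SAS because this is a parallel groups trial with repeated measures assessed over time". It then names t-tests of change within each group, t-tests between groups at 12 months, and a chi-square test for remission. It names no coach, group or wave term, and C12 does not list clustering among the limitations.

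**The concern.** This is a partially nested design: treated patients share coaches and group sessions, and controls share almost nothing. The protocol expects shared influence to do some of the work. C5a describes relationship building and group problem solving, C5e brings peer mentors into the groups, and A4d credits peer social support for the success of group programmes. Some correlation of outcomes within a group is therefore plausible on the plan's own theory.

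The repeated-measures model, as described, covers correlation within a person only. The chi-square test treats all patients as independent. If there is correlation between people in the treatment arm, the interval around the effect size will be too narrow and the 12-month tests will reject too often. Section D offers the results as pilot data for larger studies, so the next trial would also inherit no ICC from which to set a design effect.

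**Working it through.** **The plan's own figures.** 72 × (1 − 0.15) = 61.2, which reproduces the stated 61 or so completers. There is no power statement to reproduce.

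**Inputs.** Waves of 20 to 24 give 72/24 = 3.0 to 72/20 = 3.6 waves, with about 12 treated patients in each. After 15% attrition, 12 × 0.85 = 10.2. Using m = 10.2 as the cluster size assumes one treatment group per wave, which the documents do not state. The ICC is also assumed, from 0.01 to 0.10, and controls are taken as independent.

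**Formulas.**
- Treatment-arm design effect: DE = 1 + (m − 1) × ICC.
- Between-arm ratio of true to naive standard error, equal arms: R = √((DE + 1)/2).
- Within-treatment ratio: √DE.
- Amount by which the naive standard error is too small: 1 − 1/R.
- True size of a nominal 5% test: 2 × (1 − Φ(1.96/ratio)).

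**Results for m = 10.2.**

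| ICC | DE | Between-arm R | Naive SE too small by | Between-arm size | Within-treatment ratio | Within-treatment size |
|---|---|---|---|---|---|---|
| 0.01 | 1.092 | 1.02 | 2% | 5.5% | 1.05 | 6.1% |
| 0.02 | 1.184 | 1.05 | 4% | 6.1% | 1.09 | 7.2% |
| 0.05 | 1.460 | 1.11 | 10% | 7.7% | 1.21 | 10.5% |
| 0.10 | 1.920 | 1.21 | 17% | 10.5% | 1.39 | 15.7% |

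The within-treatment test is hit harder because it has no unclustered control arm to dilute the effect. For remission, the same between-arm ratio applies under the null hypothesis of equal proportions, with the ICC taken on the 0/1 scale.

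**Check by simulation** (40,000 trials per setting, three groups of 10 treated against 30 controls). The size of the naive between-arm t-test was 4.9%, 5.5%, 7.6% and 10.6% at ICC 0, 0.01, 0.05 and 0.10. The within-control test stayed at 4.7% to 5.0%.

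**Smaller clusters.** If groups were split across two coaches or the two named sites, m would be about 5. Then DE = 1 + 4 × ICC = 1.04, 1.08, 1.20 and 1.40, and R = 1.01, 1.02, 1.05 and 1.10.

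**Wave effect common to both arms.** If the only clustering is a wave effect shared by the arms (5% or 10% of variance), the naive between-arm test is slightly conservative, with a simulated size of 4.3%. The within-group tests in both arms would then be affected (within-control 10.2% at 5% of variance). That is a different mechanism from clustering in the treatment arm.

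**The case against.** The strongest reply is that the documents do not establish clusters of any known size. C8 uses waves only to describe randomisation, and nothing says that support groups are closed or formed by wave. C5f describes community cooking classes at three locations. Much of the intervention is individual: C8 lists 14 individual coaching sessions, and there are tailored texts and home-delivered food boxes. PROC MIXED could also carry a coach or group effect, so for the continuous outcomes C11 is silent rather than explicit about independence. This is a pilot with no power claim, and a variance component from about three groups has about 2 degrees of freedom (t critical value 4.30). All of this stands, and it limits the size of the problem. It does not supply the missing specification: one-to-one coaching can still cluster outcomes by coach, and the chi-square test cannot carry a cluster term.

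A reader might infer more than the documents support:

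- *That treatment groups follow recruitment waves.* This is an inference, stronger for the month 1 sessions than for the monthly groups.
- *That every Aim 2 contrast is affected.* The within-control test is not affected by treatment-arm clustering, and a shared wave effect alone makes the between-arm test conservative.
- *That the pilot's standard deviation would mislead the next trial.* It barely changes. Simulated with 31 treated patients in groups of 10, 10 and 11 against 30 controls, the pooled value is 0.996 at ICC 0.05 and 0.992 at ICC 0.10, against a true 1.0. The risk is leaving out a design effect.

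**Conclusion.** The point holds in conditional form. C11 leaves treatment-arm clustering by coach or support group unaddressed, and any positive within-group correlation makes the between-arm and within-treatment standard errors too small. With about 10 completers per group the between-arm understatement runs from about 2% at ICC 0.01 to 17% at ICC 0.10; with about 5 per group it is roughly half that or less. These figures rest on assumed ICCs and cluster sizes, neither of which the documents give. At the low end the effect is negligible; at the high end the true size of a nominal 5% test roughly doubles. The plan should be amended because the remedy is cheap and the affected quantity is the one C4e lists first. The documents do not support saying that the standard errors are certainly wrong, nor a rule that a finding counts only if it survives the whole assumed ICC range.

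**What to change.** 1. **Data.** Record coach ID, support-group ID and wave for each treatment participant, and any change of coach, since C12 foresees redistributing a coach's patients. Coaches are already assigned and attendance logs are already planned, so this is a few fields in REDCap.
2. **C11.** Prespecify a sensitivity analysis for the 12-month between-arm and within-treatment contrasts, including remission. Multiply the treatment-arm variance by DE = 1 + (m − 1) × ICC at ICC 0, 0.02, 0.05 and 0.10, using observed group sizes (for unequal groups, m = Σm²/Σm). Leave the control-arm variance as it is, and show the intervals side by side.
3. **Optional model.** Add a random coach or group effect in the treatment arm only, with Kenward-Roger or Satterthwaite degrees of freedom. This should not be mandatory with about three groups.
4. **Reporting.** Give the estimated ICC with its interval and say how imprecise it is, so that the next trial applies a design effect. With equal arms and groups of about 10, that multiplies the naive sample size by (DE + 1)/2, or 1.05 to 1.46 for ICC 0.01 to 0.10.

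The cost is a paragraph in C11 and the ID fields. The downside is wider intervals and, if there are only about three groups, a variance component too imprecise to lean on.

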**C1c. Goal.** The HEAL Diabetes study addresses a critical need to identify effective, scalable, and sustainable behavioral weight-loss approaches to help medically underserved patients in the U.S. achieve substantial weight loss and diabetes remission. We will compare primary biological outcomes (body weight, number of prescribed blood pressure medications, A1c, and diabetes remission), secondary metabolic outcomes (fasting glucose, insulin, insulin resistance, lipid profile, and CRP levels), and secondary patient-reported outcomes (self-efficacy, self-care activities related to general diet and exercise, health-related quality of life, and average pain rating) at baseline and 12-months. Based on DiRECT and MODEL study experience and evidence from other key studies and systematic reviews, we hypothesize that the HEAL Diabetes intervention will result in weight loss  $\geq 10$  kg and diabetes remission in over 40%, self-efficacy in plant-forward healthy eating will mediate its effects on primary biological outcomes, and it will be operationally and financially sustainable.

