**Table 3: Outcome Measures**

Outcome Measures	Measurement	Schedule
Primary biological outcomes (Aim 2)		
Body weight (kg)	Body weight will be measured without shoes in regular clothes using calibrated scales (Befour Model: WH1061)	Baseline, 3-, 6-, and 12-month visits
		Weekly
Blood pressure (mm Hg)	Systolic and diastolic blood pressure using automated cuffs (Omron Model: HEM-907) using a validated protocol  and number of blood pressure medications by patient report supplemented by medical record review	Baseline, 3-, 6-, and 12-month visits
A1c (%)  and diabetes remission 	Metabolic assessments obtained using standard protocols with diabetes remission defined as A1c < 6.5% after at least 2 months off all antidiabetic medications except GLP-1 agonists and SGLT-2 agonist medications, from baseline, months 6 & 12	Baseline, 6-, and 12-month visits
Secondary metabolic and patient-reported outcomes (Aims 1 and 2)		
Self-efficacy	129,130 Stanford Diabetes Self-Efficacy Scale	Baseline, 6-, and 12-month visits
Diabetes self-management	Two (out of six total) subscales of the revised Summary of Diabetes Self-Care Activities questionnaire for general diet and exercise	Baseline, 6-, and 12-month visits
Secondary sustainability outcomes (Aim 1)		
Program retention (operational sustainability)	Proportion of patients retained in study at each follow-up visit calculated by dividing the number who completed follow-up at each interval by the number expected.	3-, 6-, and 12-month visits
Cost effectiveness of the multicomponent intervention (financial sustainability)	Cost-effectiveness may be calculated using method employed by DiRECT  and recommended by Centers for Disease Control and Prevention.  Incremental total costs per patient related to primary outcomes of body weight (cost per additional kg weight loss), A1c (cost per additional unit A1c reduction), and diabetes remission (cost per additional diabetes remission) at one year calculated using an intention to treat analysis. Effectiveness measured as quality adjusted life years (QALYs) using EQ-5D. 	Following completion of data collection

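### Section C11 does not define the 12-month treatment contrast or adjust for baseline; read literally, it gives up much of the precision available for body weight

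*Combined protocol and SAP*

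**What the plan says.** Section C11 is the only place where the Aim 2 analysis is specified. Baseline, 6- and 12-month values of body weight, blood pressure, A1c and the self-care scales go into one repeated-measures analysis: "We will use the MIXED procedure of SAS because this is a parallel groups trial with repeated measures assessed over time". Two tests follow. The within-group test is explicitly on change: "t-tests within group to detect change from baseline to 12-months". The between-group test is not: "t-tests between groups to detect the effect of the treatment on the various outcome variables at 12-months". C11 calls these tests a priori and unadjusted. The same sentence goes on to Bonferroni for the intermediate visits, so the missing adjustment is for multiplicity, not for baseline.

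Three other places bear on the point without settling it:

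- C1c states its expectation in terms of loss: "we hypothesize that the HEAL Diabetes intervention will result in weight loss" of at least 10 kg.
- The cost-effectiveness row of Table 3 uses "cost per additional kg weight loss".
- C4e sets the sample size pragmatically at 72, expects that "about 61 study participants will complete the study", and lists "Effect size for the study intervention" first among the quantities the pilot is to estimate.

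**The concern.** C11 speaks of change for the within-group test and drops it for the between-group test. It also omits the mean structure, the covariance structure and any role for the baseline value in the treatment comparison. At least three estimators fit under the same heading: the difference in raw 12-month means, the difference in change from baseline, and the baseline-adjusted difference. Under randomisation all three target the same effect, but their precision can differ greatly.

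Having baseline in the MIXED model as a response does not remove the problem. If each group has its own free mean at each visit, the group contrast at month 12 is, with complete data, simply the raw difference in means. Precision is gained only if the contrast is the difference in change, or baseline means are constrained equal across arms, or baseline is a covariate. C11 states none of these.

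Two things are at stake: the precision of the effect size that the pilot is meant to supply, and the possibility that the choice among contrasts is made after the data are seen.

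**Working it through.** **The plan's own figure.** C4e: 72 × (1 − 0.15) = 61.2, which reproduces the stated 61 completers, or about 30.5 per arm.

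**Assumptions.** The documents give no SD, correlation, between-group difference, alpha or sidedness. Assumed here: two-sided 5%, 59 df, weight SD (s) 15–25 kg, baseline-to-12-month correlation (r) 0.8–0.95, equal SDs at both times, and a between-group difference of 10 kg, with 5 kg as a smaller case. The 10 kg in C1c is the loss expected with the intervention, not a difference between arms; it serves only as a reference value.

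**Formulas.** The standard error is SD × √(2/30.5), where the SD is:

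- raw 12-month means: s
- change from baseline: s√(2(1 − r))
- baseline-adjusted: s√(1 − r²)

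**Variance relative to raw means**, for any SD:

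| r | change, 2(1 − r) | adjusted, 1 − r² |
|---|---|---|
| 0.3 | 1.40 | 0.91 |
| 0.5 | 1.00 | 0.75 |
| 0.7 | 0.60 | 0.51 |
| 0.8 | 0.40 | 0.36 |
| 0.9 | 0.20 | 0.19 |
| 0.95 | 0.10 | 0.10 |

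The ratio of adjusted to change variance is (1 + r)/2: 0.65 at r = 0.3, 0.85 at 0.7 and 0.95 at 0.9. Apart from one degree of freedom, adjustment is therefore at least as precise as either alternative.

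**Body weight, worked case (s = 20, r = 0.9).** Raw SE = 20 × √(2/30.5) = 5.12 kg. Change SE = 5.12 × √0.20 = 2.29 kg. Adjusted SE = 5.12 × √0.19 = 2.23 kg. With t = 2.00, the half-widths are about 10.2, 4.6 and 4.5 kg.

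**Power (noncentral t):**

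| SD, r, difference | raw | change | adjusted |
|---|---|---|---|
| 20 kg, 0.9, 10 kg | 48% | 99.0% | 99.3% |
| 25 kg, 0.8, 10 kg | 34% | 68% | 73% |
| 15 kg, 0.8, 10 kg | 73% | 98% | 99% |
| 20 kg, 0.9, 5 kg | 16% | 57% | 60% |

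**Check that MIXED alone does not help.** Generalised least squares with three visits and 30 and 31 complete cases (s = 20, r = 0.9) gives SE 5.12 kg for the month-12 contrast with separate group means, 2.29 kg for the difference in change, and 2.23 kg with baseline means constrained equal. At s = 25, r = 0.8 the values are 6.40, 4.05 and 3.84 kg. In one fitted mixed model on simulated data with group-by-visit means, the month-12 contrast equalled the raw difference in means (−8.43 kg, SE 5.10), while the change contrast from the same fit had SE 1.74.

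**A1c (assumed SD 1.0).** Half-widths for raw / change / adjusted are 0.51 / 0.61 / 0.49 at r = 0.3 and 0.51 / 0.40 / 0.37 at r = 0.7. At the lower correlation a change contrast is the worst of the three.

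**Chance imbalance.** With 36 per arm, the probability of a baseline weight difference of 5 kg or more in either direction is 2(1 − Φ(5/(s√(2/36)))): 16%, 29% and 40% at s = 15, 20 and 25. An unadjusted 12-month comparison carries most of such an imbalance into the estimate.

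**The case against.** The strongest reply is that a change contrast is what the authors mean. C11 uses baseline data in the comparison of groups, a repeated-measures ANOVA in a parallel-group trial is ordinarily read through group-by-time, and C1c and the cost analysis speak of weight loss. On that reading weight loses almost nothing: 99.0% against 99.3% power in the worked case. This stands as a possible reading, but C11 does not state it, and the hypothesis and cost wording do not define the Aim 2 test. Change scores also would not suit an outcome with a low correlation.

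Second, the raw figures use completers only, whereas MIXED would also use baselines from participants without a 12-month value. With 36 baselines and 30.5 month-12 values per arm, data missing at random and unstructured covariance, the raw-reading SE at s = 20, r = 0.9 is 20 × √(2 × (0.19/30.5 + 0.81/36)) = 4.79 kg, or about ±9.6 kg and 54% power. C9 also allows the best available weights and A1c values within 3 months for participants who discontinue, so more than 61 may be analysed; with all 36 per arm, raw power is 55%. These corrections are right, but they narrow the gap only slightly.

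Third, this is a pilot with a pragmatic sample size and feasibility as its first aim, and every input except the 61 is assumed. That limits the consequence. It does not remove the plan's own intention to estimate an effect size and to test it a priori at 12 months.

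**Conclusion.** The concern holds as a matter of under-specification and precision. Nothing is invalidated: the literal test is unbiased, has valid type I error, and there is no power target to miss. On the literal reading, however, baseline adjustment would leave only 36%, 19% or 10% of the raw variance for weight at correlations of 0.8, 0.9 or 0.95. With an SD of 20 kg and r = 0.9, that is an interval about 20 kg wide against about 9 kg. If change is intended, the loss is small for weight but remains material where the correlation is low: adjusted variance is 15–35% below change variance for r between 0.7 and 0.3. The size rests on assumed SDs, correlations and differences. That adjustment is at least as precise as either alternative, apart from one degree of freedom, does not depend on those particular values. The change should be made, although the trial does not stand or fall on it.

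**What to change.** In C11, define the treatment effect for body weight, blood pressure and A1c as the baseline-adjusted between-group difference at 12 months. Estimate it in PROC MIXED with visit and group-by-visit terms and unstructured covariance, in one of two ways:

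- baseline kept as a response, with its mean constrained equal across arms; or
- post-baseline visits only as responses, with group, baseline value and baseline-by-visit as additional terms.

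Name which of the two is used before the data are examined, and report the 12-month difference with its 95% CI. The same definition can serve the self-care scales, which C11 analyses in the same way.

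The cost is a few sentences of analysis text. Table 3 already schedules baseline weight, blood pressure and A1c, so no visit, measurement or participant is added.
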